6.3.8 Exposure to Treatment

The duration of exposure (in weeks) to the study treatment i.e. number of weeks study drug was taken as per protocol will be summarized by treatment for the safety population (SAF).

The number and percentage of patients will be tabulated by treatment group for duration (categorized by weeks), defined as

$$(\text{Last dose date} - \text{First dose date}^* + 1) / 7$$

*First dose date is not collected in the eCRF, we will use the visit 2 date as a first dose date because it is the administration date.

Study drug compliance will be summarized for all patients in the SAF by visit, separately by treatment group. The study drug compliance is assessed at each visit by the investigator.

Additionally, the number and percentage of patients will be tabulated by visit and treatment group for compliance category (categorized in <80% and 80-100%).

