At Visit 2 (week 0), patients will be randomized to receive either sacubitril/valsartan or enalapril; patients should continue to take their background medication for HF during the study, with the exception of ACEI or ARBs – these are replaced by the study treatment and must be discontinued 36 hours before first application of the study drug. The first application of the study drug is planned for the day after Visit 2 (randomization) – therefore the last intake of the patient's ACEI or ARB before commencing study drug intake should be on the evening before Visit 2 (e.g. if Visit 2 is scheduled for Wednesday the last ACEI or ARB medication should be taken by the patient on Tuesday evening. The patient will then start to take the first dose of study medication (sacubitril/valsartan or enalapril) on Thursday morning).

Treatment will be initiated depending on the patient's previous ACEI/ARB. Refer to [Table 5-2](#)). After 2 weeks (i.e. at Visit 3) the doses are up-titrated and after another 2 weeks (i.e. at Visit 4) all patients should have achieved the target dose of either 10 mg bid enalapril or 97 mg/103 mg bid sacubitril/valsartan, provided no safety and tolerability issues arise during up-titration. The titration steps for the three dose levels are described in detail in [Section 5.5.4](#).

[figure not shown]
Note: according to the sacubitril/valsartan SmPC and the investigator's medical judgement, patients suffering from moderate hepatic impairment, moderate renal impairment or patients with SBP \geq 100 to 110 mmHg should be initiated at dose level 1.

At this visit the baseline actigraphy data will be downloaded from the wrist-worn device.

Visit 3 to Visit 6

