5.5.8 Prohibited medication

Use of the treatments displayed in [Table 5-3](#) is NOT allowed after the start of the washout period, i.e. the evening before Visit 2. Note, during the baseline recording period, i.e. over two weeks after Visit 1 (i.e. week -2 until 12 hours before Visit 2) the patients will receive their usual pre-study medication to obtain a baseline.

ACEIs and/or ARBs are replaced by study medication and therefore need to be discontinued 12 hours before Visit 2 (i.e. the evening before Visit 2). At Visit 2, patients will be randomized to receive either sacubitril/valsartan or enalapril; the patients will receive the first dose of study medication 24h after the randomization visit, resulting in a washout period from ACEIs or ARBs of 36 hours. In order to avoid excessive RAAS inhibition, it is crucial to respect the washout period and instruct the patient to not take any ACEI or ARB while taking double-blind study medication.

Direct renin inhibitors (i.e. aliskiren) are also prohibited for safety reasons, as concomitant intake of renin inhibitors and study medication could increase the likelihood of occurrence of hyperkaliemia.

Bile acid sequestering agents are prohibited due to potential interference with the absorption of study drugs.

Table 5-3 Prohibited medication

Medication	Action taken
Any ACEI, Any ARB, Renin inhibitors	Discontinue these drugs starting at 12h before Visit 2, prohibited until at least 36 hours after study drug discontinuation/interruption/end of study. In case these drugs are taken / need to be taken during the double-blind treatment period of the study, discontinue study drug.
Bile acid sequestering agents (e.g. cholestyramine, colestipol)	Discontinue before randomization, prohibited throughout the study. No action required with study medication.

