Visit Window	-3/+1		-3/+3	-3/+3	-5/+5	-1/+5				the interval between the visits must not exceed 35 days as study comes in pre-filled packages for 35 days of treatment

³ Study Medication will be dispensed but not be taken until the next day

⁴ Only if no ECG has been performed within the last 3 months

assessments not required by the protocol, however if available within the diagnostic routine, they should be entered in the study data base

uns – unscheduled visit; when deemed necessary, unscheduled visits may be performed to ensure adequate medical management. This is exemplified by, but not limited to, patients achieving target dose at visit 4 and are perceived as fragile and thus need an extra monitoring visit, NYHA IV, renal impairment, patients prone to hypotension and or hepatic impairment. Investigator's clinical judgement and discretion is advised.

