4 OVERALL STUDY DESIGN

4.1 Overview of Study Design

This is an international (European), randomized, actively controlled, double-blind, double-dummy, interventional study with prospective data collection. The study comprises 6 visits over 14 weeks. Adult patients with symptomatic HFREF (NYHA classes II or III/IV at a 1:1 ratio) managed in an ambulatory setting (i.e. by primary care physicians, office based cardiologists, HF outpatient clinics) will be randomized in a 1:1 allocation to receive sacubitril/valsartan or enalapril during the double-blind period. Actigraphy will be performed during the entire duration of the study by means of a wrist-worn accelerometry device; the device will be worn continuously for two weeks prior to randomization in order to obtain an individual baseline for each patient, and throughout the treatment period of the study (12 weeks). Figure 4-1 depicts the study design along with the treatment and visit schedule.

Figure 4-1 Study design

¹⁻² sacubitril/valsartan or enalapril (double-blind study drugs) will be given at dose levels (up-titration) depending on pre-study ACEI/ARB doses.

³Pre-study ACEI and/or ARB are replaced by study medication after Visit 2. Therefore washout period (WO) of 36 hours is required; it should start 12 hours before Visit 2 (randomization); the first study treatment intake should be 24 hours after Visit 2. All other HF background and CV medications (e.g. beta blockers, MRAs etc.) and symptomatic treatment (e.g. diuretics) the patient has been taking should remain unchanged throughout the study, if possible and medically justified in the judgement of the investigator.

"Background HF medication per local practice": patients must be on stable HF treatment regimen for at least 4 weeks prior Visit 1. After Visit 1, patients shall retain their pre-study HF treatment for another 2 weeks (week -2 to week 0) for baseline actigraphy recording.

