6.3.10 Adverse Events

Treatment emergent adverse events TEAEs (events started on or after the first dose date of study treatment or events present prior to the first dose of study treatment but increased in severity based on preferred term) will be summarized. Only primary paths within MedDRA will be considered for TEAEs reporting.

TEAEs will be summarized by presenting, for each treatment group, the number and percentage of subjects

- having any TEAEs,
- having a TEAEs in each primary system organ class and

- having each individual TEAEs (preferred term).

Summaries will also be presented for TEAEs by severity and for study treatment related TEAEs. If a subject reported more than one adverse event with the same preferred term, the adverse event with the greatest severity will be presented. If a subject reported more than one adverse event within the same primary system organ class, the subject will be counted only once with the greatest severity at the system organ class level, where applicable.

Separate summaries will be provided for death, serious adverse event, adverse events leading to discontinuation and adverse events leading to dose adjustment (including study treatment discontinuation).

A listing of all AEs will be presented, whether treatment emergent or not.

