For the analyses of further secondary and of the exploratory endpoints referring to data at 'end of study' the same algorithm will be applied to create an extra LOCF visit next to the usual Week 12 visit. This additional 'end of study' measure constitutes a conservative approach in handling of missing data and ensures much as possible unbiased and comparable efficacy results.

In case of qualitative (e.g., increased level of non-sedentary daytime physical activity) or semi-quantitative (e.g., PGA) efficacy variables, missing Week 12 values of patients previously dropped out due to hospitalization or death will be substituted by the worst value possible for the respective variable (e.g., increased level of non-sedentary daytime physical activity="No", PGA="much worse").

In the event that any date for Adverse Events is incomplete after Data Management processing and this date needs to be used for a calculation, the following will be assigned for the missing date:

- if no field is available: no imputation will be performed
- if only the year is available:
 - Onset date: day "01" and month of "January" or first dose administration date, whatever occurs after will be imputed
 - End date: day "31" and month of "December" or EOS date, whatever occurs before will be imputed
- if the month and year are available:
 - Onset date: day "01" will be imputed
 - End date: "last day of the month" will be imputed

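### Month-only adverse event onsets lack the first-dose check that year-only onsets have, and the SAP dates first dose one day before planned intake, so treatment-emergent events are misclassified

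*SAP*

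**What the plan says.** **Treatment-emergent definition.** SAP 6.3.10 counts "events started on or after the first dose date of study treatment", together with events already present that worsen in severity. Protocol 9.5.2.1 uses onset after the first dose.

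**Partial onset dates (SAP 6.6).** If only the year is known, the onset becomes 1 January or the "first dose administration date, whatever occurs after will be imputed". If month and year are known, the rule is only "Onset date: day '01' will be imputed". The second rule makes no comparison with first dose.

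**First dose date.** SAP 6.3.8 states that the date is not collected in the eCRF and continues: "we will use the visit 2 date as a first dose date because it is the administration date". Four other places put first intake on the next day:
- Protocol 3.1 (Visit 2): "The first application of the study drug is planned for the day after Visit 2 (randomization").
- Protocol 5.5.8: "the patients will receive the first dose of study medication 24h after the randomization visit".
- Protocol Table 6-1, footnote 3: "Study Medication will be dispensed but not be taken until the next day".
- SAP 4.1, footnote to Figure 4-1: "the first study treatment intake should be 24 hours after Visit 2".

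**The concern.** The SAP protects the less precise date (year only) against falling before first dose, but not the more precise one (month and year). Followed as written, a reaction that began in the first days of dosing and was recorded only by month moves to before treatment and leaves the treatment-emergent tables.

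The reason given for the Visit 2 proxy is contradicted by the protocol and by the SAP itself. The proxy is stated under exposure, and SAP 6.3.10 does not refer to it. It is, however, the only working first dose date in the SAP, so by inference it also governs the treatment-emergent rule. New events on the Visit 2 day would then count as treatment-emergent in patients who had not yet taken study drug. The baseline 6-minute walk is done at that visit.

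The two faults run in opposite directions and affect different events. The proxy shifts the start of the window and adds pre-dose events. The day-01 rule shifts the event and removes on-treatment ones. SAP Tables 14.3.1-1 to 14.3.1-6 all depend on this classification. The removals fall almost entirely in the first month, which contains initiation and up-titration (Protocol 5.5.4).

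**Working it through.** **1. Planned first intake.** SAP 4.1 gives a 36-hour washout that starts 12 hours before Visit 2, with first intake 24 hours after it. 12 + 24 = 36, so the figure reproduces and Visit 2 is a pre-dose day by plan.

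**2. Exposure.** The SAP 6.3.8 formula is (last dose date − first dose date + 1) / 7. Number the Visit 2 day as day 1 and take last dose on day 84.
- First dose = day 1: (84 − 1 + 1)/7 = 12.00 weeks.
- First dose = day 2: (84 − 2 + 1)/7 = 11.86 weeks.
- Difference: 1/7 = 0.14 week, or 1/84 = 1.2%.

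**3. Day-01 rule, one patient.** Visit 2 on 15 March, first intake 16 March. Every month-only onset from 16 to 31 March (16 days) is imputed to 1 March. Since 1 March is before 15 March, none is treatment-emergent by onset. That is 16 of the first 28 on-treatment days (57%). Onsets in April or later are imputed to a date after dosing and are unaffected.

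**4. Day-01 rule, averaged.** The documents do not give Visit 2 or onset dates. I assume that both are spread evenly, and enumerate all 1,461 Visit 2 dates from 1 January 2017 to 31 December 2020. On-treatment days run from Visit 2 + 1. An onset is lost when day 01 of its month is before Visit 2, the SAP's first dose date.

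| On-treatment days | Mean days lost per patient | Share of month-only onsets lost |
|---|---|---|
| 1 to 14 | 10.09 | 10.09/14 = 72.1% |
| 1 to 28 | 13.74 | 13.74/28 = 49.1% |
| 1 to 84 | 13.76 | 13.76/84 = 16.4% |

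With 83 days as the denominator the last share is 16.6%. By Visit 2 date, the 84-day share runs from 0% (Visit 2 on the 1st, 3.3% of dates) to 29/84 = 34.5%.

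**5. The same enumeration with the fix.** Month-only onsets in the month of first dose are set to Visit 2 + 1, and all others to day 01. On-treatment onsets lost: 0%. The price is paid on month-only onsets that truly fell between 14 days before Visit 2 and the Visit 2 day. Those counted as treatment-emergent rise from 0.2% under the SAP rule to 73.7%, before any limit from known end dates.

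**6. Year-only rule.** Taking the later of 1 January and first dose moves an onset from the previous calendar year to first dose. That can matter only when screening crosses 1 January: 14/365 = 3.8% of patients under even enrolment. The Visit 1 window of −3/+1 days makes this 13/365 = 3.6% to 17/365 = 4.7%.

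**The case against.** The strongest counter-argument concerns size. Every percentage above is a share of month-only onsets, and the documents do not say how many there are. SAP 6.6 applies the rule only to dates still incomplete after data management and needed for a calculation. Protocol 7.1 asks for start and end dates and for questioning at each visit, and Protocol 8.3 provides for site queries. Visits 3 and 4 come at weeks 2 and 4, so recall should be best in the weeks where the loss is greatest. Even spread may therefore overstate it. This is plausible but cannot be tested from the documents.

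There are also safeguards. SAP 6.3.10 counts subjects, so one lost event need not remove a patient from a row. All events are listed, worsening events still count, and the listings of deaths, serious events and events leading to discontinuation (14.3.2-1 to 14.3.2-4) are not titled as treatment-emergent only. Both arms follow the same rules. Opening the window at Visit 2 errs towards inclusion.

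Finally, the fix replaces under-inclusion by over-inclusion, as step 5 shows.

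These points limit the consequence and all of them stand. None supplies the missing comparison or reconciles the Visit 2 date with the planned intake.

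**Conclusion.** The concern holds. Followed exactly, SAP 6.6 classes some on-treatment events as not treatment-emergent, and SAP 6.3.8 overstates exposure by one day (0.14 week) in each patient dosed as planned. The day-01 rule is the main fault. It affects 16.4% of month-only onsets over 84 days, 49.1% in the first 28 days and 72.1% in the first 14, assuming even spread of Visit 2 dates and onsets. The absolute number of events cannot be stated.

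That Visit 2 also opens the treatment-emergent window is an inference, though the SAP offers no other date. The overall effect is on the counts in the treatment-emergent tables and on exposure. It is likely to be small, with no evident bias between arms and no effect on efficacy. The change should still be made, because the rules contradict the documents' own schedule and the repair is cheap.

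**What to change.** - **SAP 6.6, month and year known:** if the month is that of first dose, impute the first dose date; otherwise impute day 01. Never impute an onset later than a known end date.
- **SAP 6.3.8:** for analysis, derive first dose as Visit 2 date + 1 day, or use the actual date where one is recorded (for example an early intake captured in the dose administration record, Protocol 7.8). Use this one date for exposure and for SAP 6.3.10, so that these sections agree with SAP 4.1 and the protocol.
- **Tables 14.3.1-1 to 14.3.1-6:** footnote the number of events classified by an imputed onset.
- **Minor clean-up:** apply the year-only comparison with first dose only when the recorded year is the year of first dose.

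The cost is a few sentences and a small change to the derivation, with no new data. The SAP should say openly that over-inclusion is a choice. Some screening-period events with month-only dates will count as treatment-emergent; the end-date limit reduces this and the footnote makes it visible. Visit 2 + 1 is also a planned date, so an unrecorded early intake would lose that day's events. Amendment 4 reports that the last patient's last visit has taken place. The number of month-only onsets in the first-dose month can therefore be counted at the blind review (SAP 6.2) before database lock, which would settle how much this matters.

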6.3.9 Concomitant Medication

Concomitant medications will be summarized by the preferred term as coded by the World Health Organization Drug (WHODRUG) dictionary for the SAF population.

6.3.10 Adverse Events

Treatment emergent adverse events TEAEs (events started on or after the first dose date of study treatment or events present prior to the first dose of study treatment but increased in severity based on preferred term) will be summarized. Only primary paths within MedDRA will be considered for TEAEs reporting.

TEAEs will be summarized by presenting, for each treatment group, the number and percentage of subjects

- having any TEAEs,
- having a TEAEs in each primary system organ class and

- having each individual TEAEs (preferred term).

Summaries will also be presented for TEAEs by severity and for study treatment related TEAEs. If a subject reported more than one adverse event with the same preferred term, the adverse event with the greatest severity will be presented. If a subject reported more than one adverse event within the same primary system organ class, the subject will be counted only once with the greatest severity at the system organ class level, where applicable.

Separate summaries will be provided for death, serious adverse event, adverse events leading to discontinuation and adverse events leading to dose adjustment (including study treatment discontinuation).

A listing of all AEs will be presented, whether treatment emergent or not.

6.3.11 Liver Events

Number and percentage of patients with liver events and information related with the events will be tabulated

A listing of all liver events will be presented.

6.3.12 Renal Events

Number and percentage of patients with renal events and information related with them will be tabulated

A listing of all renal events will be presented.

6.3.13 Other Safety Assessments

Vital Signs

Analysis of the vital sign (blood pressure and pulse) measurements using summary statistics for the change from baseline for each post-baseline visit will be performed. These descriptive summaries will be presented by vital sign and treatment group. Change from baseline will only be summarized for subjects with both baseline and post-baseline values. All information collected will be listed by subject and abnormal values be flagged.

Clinical Laboratory Measurements

Laboratory data will be summarized by presenting shift tables using extended normal ranges (baseline to most extreme post-baseline value), by presenting summary statistics of raw data and change from baseline values (mean, medians, standard deviations, ranges) and by the flagging of notable values in data listings.

Clinically notable laboratory abnormalities for selected tests based on a percent change from baseline.

Hemoglobin > 50 % increase, > 20 % decrease

ALT > 150 % increase

AST > 150 % increase

Creatinine > 50 % increase

Potassium > 20 % increase, > 20 % decrease

6.4 Level of Significance, Multiple Comparisons and Multiplicity

All statistical hypotheses will be two-sided and will be performed using a 5% significance level.

No adjustment for multiple comparisons or corrections for multiplicity are planned.

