9.4 Analysis of the primary variable(s)

9.4.1 Variable(s)

There are two primary variables. The physical activity primary variable is the change in walking distance in meters from baseline to visit 6 as assessed by the 6 minute walk test. The actigraphy primary variable is the change from baseline to 'end of study' in mean daily non-sedentary daytime activity (defined as ≥ 178.50 counts per minute) as calculated by the MotionWatch 8 accelerometer device. Baseline is defined as the average min per day in non-sedentary daytime activity over 2 weeks (week -2 to week 0) prior to randomization and 'end of study' is defined as the average minutes per day in non-sedentary daytime activity between week 10 to week 12.

The aim of the primary analysis of this study is to assess differences between sacubitril/valsartan and enalapril patients with respect to the primary endpoint in the FAS.

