9.5 Analysis of secondary variables

9.5.1 Efficacy variables

For the secondary variable is the proportion of patients with increased level of non-sedentary daytime physical activity at 'end of study' compared to baseline. It will be analyzed by applying a logistic regression model with factors treatment and baseline NYHA class (NYHA II vs. III/IV) and the baseline value as further covariate. The Odds Ratio for the factor treatment and its 95%-confidence interval will be given. The analysis of this secondary variable will be performed in the FAS (with and without imputation of missing values described in [Section 9.4.3](#).) and additionally in the PP population with and without imputation of missing values.

All other secondary efficacy variables will be analyzed descriptively using the statistics for continuous and categorical data described in [Section 9](#) above. Additionally, two-sided tests of significance (with $\alpha = 0.05$) between the two treatment groups will be performed for all secondary endpoints, using appropriate testing procedures. Details to those statistical testing procedures will be defined in the SAP.

All statistical tests of secondary efficacy variables will be on an exploratory basis. Therefore, no multiple testing strategy will apply for these tests

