9.8 Sample size calculation

There are no published data on a possible effect of a drug intervention on physical activity in HFrEF patients. However, Alosco and colleagues observed patients with HF over a period of 12 weeks and reported activity levels at baseline and after 12 months using a similar accelerometry device (Alosco et al., 2015). The mean activity time in light intensity was 188 min/day (SD = 56) at baseline and 183 min/day (SD = 58) after 12 weeks. The corresponding values for activity in moderate to vigorous intensity were 46 min/day (SD = 35) at baseline and 41 min/day (SD = 30) after 12 weeks. From these data an average of 234 min/day at baseline and 224 min/day after 12 weeks can be concluded for the non-sedentary daily activity time. The observed standard deviations for sedentary daily activity time were 76 min/day (baseline) and 63 min/day (month 12), respectively. From these values the standard deviation for non-sedentary activity time (which is approximately the same as for sedentary activity time) is estimated as SD = 70 min/day for both time points.

For the present study we assume a mean baseline value of 200 to 230 min/day for both treatment groups. If treatment with sacubitril/valsartan leads to an improvement which is at least 20 min/day higher than the changes under enalapril, this is considered as clinically relevant.

The standard deviation for the changes from baseline is expected not to be larger than the standard deviations at the two respective visits (corresponding to a correlation coefficient of 0.5 between the values at baseline and at week 12 to 14). Accordingly, the standard deviation for the primary endpoint is estimated as SD = 70 min/day for both treatment groups.

Planning a two-sided test (using the t-test model with $\alpha = 5\%$ and 90% power at $\Delta = 20$ min/day) results in 259 patients per treatment group (nQuery Advisor® 7.0). In order to account for non-eligible patients, it is planned to recruit 300 patients per treatment arm, i.e. 600 patients in total.

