With respect to other primary endpoint "change in 6-minute walk test between baseline and weeks 4, 8 and 12/week 12", the following sample size considerations apply: From Täger et al. we deduce a minimal important difference of 35 meters at week 12 and a standard deviation of 114 meters ([Täger, Hanholz et al. 2014](#)). Planning a two-sided test with $\alpha = 0.05$ and 90% power for a group difference of 35 meters leads to a sample size of 224 patients per group, which is covered by the planned patient numbers.

After defining the primary hypotheses H1 and H2, to control the familywise error rate at level 5%, the Hochberg procedure will be used to test the primary hypotheses. It will reject both H1 and H2, if both of them are significant at level 5% simultaneously. Otherwise, it will reject H1 if it is significant at level $\alpha/2$, or reject H2 if it is significant at level $\alpha/2$.

Table 9-1 Power of the study considering both the end-points – Considering 259 subjects in each arm

Correlation between the two end-points	Power to reject H1	Power to reject H2	Power to reject any of H1 and H2	Power to reject both of H1 and H2
0	89.7%	93%	98.5%	84.4%
0.2	89.5%	93%	97.6%	85%
0.4	89.4%	93%	96.5%	85.7%
0.5	89.3%	93%	96%	86%

For power calculations, H1 is based on accelerometry data end-point while H2 is based on the 6 minutes walking test end-point.

Table Error! No text of specified style in document.-2 Power of the study considering both the end-points – Considering 300 subjects in each arm

Correlation between the two end-points	Power to reject H1	Power to reject H2	Power to reject any of H1 and H2	Power to reject both of H1 and H2
0	93.6%	96.2%	99.4%	90.4%
0.2	93.5%	96%	99%	90.6%

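### SAP 6.4 rules out any multiplicity adjustment, contradicting the Hochberg rule for the two primary hypotheses in SAP 4.2 and protocol 9.8

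*SAP*

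**What the plan says.** Protocol 9.4.1 states "There are two primary variables": the change in 6-minute walk distance and the change in mean daily non-sedentary daytime activity.

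SAP 4.2 says that "to control the familywise error rate at level 5%, the Hochberg procedure will be used to test the primary hypotheses", and protocol 9.8 says the same. The decision rule follows: "It will reject both H1 and H2, if both of them are significant at level 5% simultaneously"; failing that, either hypothesis can be rejected alone at half of alpha. Here H1 is the accelerometry endpoint and H2 the walk test.

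SAP 6.4 says something different: "All statistical hypotheses will be two-sided and will be performed using a 5% significance level". Its next sentence is "No adjustment for multiple comparisons or corrections for multiplicity are planned". Neither sentence exempts the primary hypotheses.

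Three other sections bear on the point:

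- SAP 6.3.5, which specifies both primary ANCOVAs, mentions neither Hochberg nor a 2.5% threshold.
- SAP 6.1, which lists changes to the planned analyses, does not say that Hochberg has been dropped.
- Protocol 9.5.1 waives adjustment, but only for secondary endpoints: "All statistical tests of secondary efficacy variables will be on an exploratory basis. Therefore, no multiple testing strategy will apply for these tests".

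**The concern.** The SAP contains two current rules for the confirmatory decision, and they can give different answers. Suppose the walk test gives p = 0.04 and accelerometry gives p = 0.30. Under SAP 6.4 the walk test is a confirmatory success. Under SAP 4.2 and protocol 9.8 it is not.

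That pattern is foreseeable. The rationale for protocol Amendment 4 doubts whether accelerometry is sensitive enough in heart failure, so a result carried by the walk test alone is a realistic outcome. The same amendment made the walk test primary after last patient last visit. In that setting the success rule should be beyond dispute before unblinding. As the SAP stands, someone who wanted the claim could cite 6.4, and someone who rejected it could cite 4.2.

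A programmer working from SAP section 6, where the analyses are specified, would find no correction to apply.

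**Working it through.** **Inputs.** All come from protocol 9.8, repeated in SAP 4.2.

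- Accelerometry (H1): difference 20 min/day, SD 70.
- Walk test (H2): difference 35 m, SD 114.
- Two-sided alpha 0.05, power 90%, 1:1 allocation; power tabulated for 259 and 300 per arm.
- Correlation between the endpoints: 0, 0.2, 0.4 and 0.5, as in the power tables.

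**Step 1: the stated sample sizes.** With n = 2(1.960 + 1.282)² × SD²/difference² per arm:

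- H1: 2 × 10.51 × (70/20)² gives 258.
- H2: 2 × 10.51 × (114/35)² gives 223.

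The noncentral t version gives 259 and 224, exactly as stated.

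**Step 2: which rule the power tables use.** Four million pairs of correlated normal test statistics were simulated, with critical values 1.960 (5%) and 2.241 (2.5%). Power to reject at least one hypothesis:

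| Per arm | Correlation | Stated | Hochberg | Unadjusted 5% |
|---|---|---|---|---|
| 259 | 0 | 98.5% | 98.6% | 99.4% |
| 259 | 0.2 | 97.6% | 97.7% | 98.9% |
| 259 | 0.4 | 96.5% | 96.6% | 98.2% |
| 259 | 0.5 | 96% | 95.9% | 97.7% |
| 300 | 0 | 99.4% | 99.5% | 99.8% |
| 300 | 0.5 | 97.8% | 97.9% | 98.9% |

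Under Hochberg every entry of protocol Table 9-1 reproduces within 0.3 percentage points, and every entry of Table 9-2 within 0.1. The unadjusted figures do not match. The trial was planned on Hochberg.

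**Step 3: familywise error with uncorrelated endpoints.** Under the global null:

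- Unadjusted: 1 − 0.95² = 0.0975.
- Hochberg: at least one p ≤ 0.025, or both between 0.025 and 0.05: (1 − 0.975²) + 0.025² = 0.049375 + 0.000625 = 0.0500.
- Difference: exactly one p between 0.025 and 0.05 and the other above 0.05: 2 × 0.025 × 0.95 = 0.0475, and 0.0500 + 0.0475 = 0.0975.

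The whole excess therefore comes from the one pattern in which the two rules disagree.

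**Step 4: familywise error over the documents' correlation range.**

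| Correlation | SAP 6.4 as written | Hochberg |
|---|---|---|
| 0 | 9.75% | 5.0% |
| 0.2 | 9.6% | 5.0% |
| 0.4 | 9.3% | 4.9% |
| 0.5 | 9.1% | 4.8% |

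Relative to the 5% that both documents promise, the unadjusted rate is 9.75/5 = 1.95 times at correlation 0 and 9.1/5 = 1.8 times at 0.5.

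**The case against.** The best defence is that SAP 6.4 is a loosely scoped sentence and not a change of plan. Hochberg is stated with its decision rule in both documents, the power tables follow it, and the SAP presents itself as adding detail to the protocol's analyses. Protocol 9.5.1 waives adjustment for secondary tests, which is probably what 6.4 was meant to echo. On this reading, anyone who applied 6.4 to the primaries would be departing from the protocol. This is likely the intent, but it is an inference. The waiver in protocol 9.5.1 is limited to secondary endpoints, that in SAP 6.4 is not, and neither document says which section prevails.

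A second defence is that the Amendment 4 rationale calls the walk test co-primary. If both endpoints had to succeed, no adjustment would be needed. The decision rule excludes this reading: it allows one hypothesis to be rejected alone, and the tables report power to reject either.

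Three further points stand and limit the finding:

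- The 5% level in SAP 6.4 is not itself the conflict. Protocol 9.4.2 also sets 0.05 two-sided, which is compatible with Hochberg at a familywise 5%. The conflict lies in the sentence that excludes any correction.
- The rules differ for one pattern of p-values only. Under the design assumptions with 300 per arm, power to reject at least one hypothesis changes by about 0.3 to 1.0 percentage points.
- The inflation shrinks as correlation rises. At 0.8, an assumed value outside the documents' range, the unadjusted rate is 7.8%.

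**Conclusion.** The concern holds. SAP 6.4 contradicts SAP 4.2 and protocol 9.8 on the confirmatory rule, and nothing else in either document resolves it. If SAP 6.4 is followed as written, the familywise error rate is 9.1% to 9.75%, against the 5% that the same SAP claims to control. If the Hochberg text is followed, control is intact and SAP 6.4 is simply wrong.

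The figures assume a true null for both endpoints, two-sided tests, approximately bivariate normal test statistics, and correlations of 0 to 0.5. They take no account of multiple imputation or of the walk-test exclusions in SAP 6.3.5. The contradiction itself rests on none of these assumptions.

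This needs correction before unblinding, because it determines what counts as a positive trial.

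**What to change.** Replace the no-adjustment sentence in SAP 6.4 with wording such as:

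*The two primary hypotheses are tested with the Hochberg procedure at a familywise two-sided alpha of 0.05. Both are rejected if both p-values are at most 0.05; otherwise a hypothesis is rejected only if its p-value is at most 0.025. Secondary and exploratory tests are performed at a nominal two-sided 5% without adjustment.*

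Add a cross-reference to this rule in SAP 6.3.5, so that the section specifying the primary analyses carries the decision rule.

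The cost is a few sentences in the SAP, which section 1 says is to be finalised before the database is closed. If it has already been signed off, a dated SAP amendment before unblinding would serve. Sample size and power tables stay as they are, since they already assume Hochberg. Repeating the rule in protocol 9.4.2 would be tidy but is not needed: protocol 9.8 already contains it, and under protocol 11.1 a protocol change requires a formal amendment with the associated approvals.
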